### **10.2. Data Analysis Considerations**

#### **10.2.1. Analysis Populations**

##### **Intention-To-Treat (ITT) Population**

All enrolled participants who take at least one dose of study medication will be included in the ITT population. Participants will be summarized by randomized treatment group.

This will be the population for all PD parameters.

## **Safety Population**

All participants who enroll in the study and receive at least one dose of study treatment will be included in the Safety Population. Participants will be summarized by actual treatment group.

This will be the population for the safety analyses, as well as for presentation and summarization of baseline/demographic characteristics.

## **Pharmacokinetic Population**

The PK Population will include all participants who undergo plasma PK sampling and have evaluable concentration-time data for analysis.

## **Pharmacodynamic Population**

The PD population will include all participants who have baseline measure, along with a post baseline measure and receive at least one dose of study treatment.

## **Open-Label Extension Population**

The OLE population will include all participants who enroll in the OLE and receive at least one dose of study treatment in the OLE.

## **12-Week Follow up Population**

The 12-Week Follow up Population will include all participants who receive at least one dose of study treatment in Part 1 and decline participation in the OLE but continue with the 12-week follow up period.

### **10.2.2. Interim Analysis**

An interim analysis will occur after the last subject completes the Week 7 visit of the study. All endpoints will be evaluated for this analysis. A final analysis will occur when the last subject completes or discontinues the study. Since this analysis is occurring at the end of the double-blind treatment phase, no adjustments of the alpha level are necessary. This analysis will serve as the primary analysis and a second analysis will occur, summarizing the endpoints after the treatment-free phase.

### **10.3. Final Analysis**

Final analysis will be performed after the completion of the study and the database is locked.

Data will be listed and summarized. Treatment will be assigned based on the dosing schedule and included in the data listings. Listings will be sorted by participant, day, and time; summaries will be presented by treatment, day, and time.

Unless stated otherwise, descriptive summaries for continuous variables will include n, mean, standard deviation (SD), median, first and third quartiles, minimum, and maximum. The geometric mean with associated 95% confidence interval (CI), and the between-participant CV (%CVb) for PK parameters only will also be included. For categorical variables, n and percent will be used as summary statistics. Baseline is the last available assessment prior to time of the first dose unless it is specified otherwise. If there are multiple assessments collected on the same scheduled time, the average of these assessments will be used. For tabulated safety summaries, only the scheduled assessments will be included in the summary tables.

Version 9.4 or higher of the SAS system will be used to analyze the data as well as to generate tables, figures, and listings.

Complete details will be documented in the Statistical Analysis Plan (SAP), which will be signed off prior to the lock of the study database.

### **10.3.1. Primary Endpoint for Efficacy**

The primary endpoint will be defined as the percentage change from Baseline in the IgG parameter at Week 7. The endpoint will be summarized using a 6-number summary including the sample size, mean, standard deviation, median, minimum and maximum values. Treatment group comparisons between the two active (separately) to the placebo arm will be performed using an Analysis of Covariance model with treatment and baseline value in the model. An alpha of 0.05 will be used to determine statistical significance.

### **10.3.2. Secondary Endpoints for Efficacy**

The secondary endpoints for efficacy are Immunogenicity determined by percentage change from Baseline in anti-RVT-1401 antibodies and characterization of any anti-RVT-1401 antibodies to confirm neutralization potential at Week 7.

For each of the continuous secondary endpoints, the actual value, change from baseline and percentage change from baseline for all secondary endpoints will be summarized by visit and treatment group using the n, mean, SD, median, first and third quartiles, minimum, and maximum values. The comparison of the active arms (separately) to the placebo arm will be performed using an Analysis of Covariance model with treatment and baseline value in the model. An alpha of 0.05 will be used to determine statistical significance. If deemed appropriate, the two active arms may be combined and compared to placebo to evaluate any treatment effect.

For categorical secondary endpoints, the number of participants who meet the endpoint and the percentage will be summarized. The percentage will be calculated using those participants who had a value at the time point. Statistical testing may be performed between the two treatments using a Fishers Exact Test. If deemed appropriate, the two active arms may be combined and compared to placebo to evaluate any treatment effect.

### **10.3.3. Safety Analyses**

Safety will be evaluated by assessment of clinical laboratory tests, physical examinations, vital signs measurements, and ECG readings at various time points during the study, and by the documentation of AEs.

AE verbatim text will be coded and classified by body system and preferred (coded) term using the MedDRA. All AEs, both serious and non-serious will be listed. AE summaries by study part and treatment group, of the number and percent of participants reporting each event at least once will be generated.

Clinical chemistry, hematology, and urinalysis values will be listed for each participant and flagged high or low relative to the normal range where appropriate. Descriptive summary statistics will be created by study part, treatment and assessment time.

Other safety data will be summarized descriptively by treatment and time. Details will be provided in the SAP.

### **10.3.4. Pharmacokinetic Analyses**

Serum compound concentration-time data will be analyzed by non-compartmental methods with Phoenix WinNonlin or other PK software programs. Calculations will be based on the actual sampling times recorded during the study. From the plasma concentration-time data, the following primary PK parameters will be determined (if possible):

AUC(0-t), Cmax, tmax, Ctrough

Additional PK parameters may be calculated. PK data will be presented in graphical and tabular form and will be summarized descriptively.

[figure not shown]
### **10.3.5. Pharmacodynamic Analyses**

All participants in the ITT population will be included in the summaries of PD data. The actual value, change from baseline and percentage change from baseline for all PD parameters will be summarized by visit and treatment group using the n, mean, SD, median, first and third quartiles, minimum, and maximum values. Statistical testing may be performed between the two treatment groups using mixed models. Details will be provided in the Statistical Analysis Plan.

Serum IgG, IgG subclass (1-4), and anti-AChR levels will be summarized as both raw values as well as percent change from baseline (intra-participant assessment). Additional PK/PD and PD/PD relationships may be evaluated. PD data will be presented in graphical and tabular form and will be summarized descriptively.

The comparison of the active arms (separately) to the placebo arm will be performed using an Analysis of Covariance model with treatment and baseline value in the model. An alpha of 0.05 will be used to determine statistical significance.

### **10.3.6. Other Analyses**

#### **10.3.1. OLE and Follow up Analyses**

Data listings and summaries will be provided separately for the OLE and 12-Week Follow up Populations. Descriptive Analyses will be presented by randomized treatment assignment from the double-blind treatment period and overall. Baseline will be specified in the Statistical Analysis Plan. If there are multiple assessments collected on the same scheduled time, the average of these assessments will be used. Only the scheduled assessments will be included in the summary tables. All OLE and follow up analyses will be based on the OLE and 12-Week Follow up Populations, respectively. Ad hoc statistical analyses such as two sample t-test or Chi-Square test, may be performed for the changes or shifts at weeks 8, 10, and 12 separately. The significance will be evaluated at a 0.05 two-sided level for informational purposes only.

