### **Expected Treatment Effect**

[figure not shown]
The proposed dosing regimens are expected to provide a sustained total IgG reduction of approximately 75-80% and 65-70% for Regimen A and B respectively, following the fourth or fifth dose. It is expected that the nadir IgG reduction will occur by the 5th dose and be maintained following the sixth dose before rising back to baseline over the next 6 to 8 weeks. These assumptions are supported by preliminary PD results, shown in Figure 1, from the ongoing Phase 1 clinical study RVT-1401-1001 (Section 3.2.3). In healthy participants, 4 weekly SC injections of 680 mg of RVT-1401 produced an average total IgG percent reduction from baseline of 78%.

For participants that enter into the OLE, IgG levels will rise over the 2-week interval between week 6 and the start of OLE dosing at week 8. The IgG levels are expected to oscillate between decreasing and increasing over the next 3 doses, with trough IgG levels expected to rise by 15-25% above the nadir levels achieved during the treatment phase in the double-blind part of the study. Subjects who switch to 340 mg every 2 weeks from the placebo treatment are expected to achieve an IgG reduction of approximately 35-45% after the last OLE dose. Upon completion of OLE dosing, all subject IgG levels are expected to return to baseline over the next 6-8 weeks.

In study RVT-1401-1001, the inter-individual variability in IgG reduction and PK was larger in the 340 mg cohort vs. the 680 mg cohort; this difference can be explained by lower receptor occupancy in the 340 mg cohort throughout the dosing interval across all individuals. It is also noteworthy that, with both doses, the variability in exposure decreased with repeat dosing. This may indicate that full receptor occupancy is not lost within the dosing interval, and that with subsequent doses, more receptors are being occupied or remain occupied.

In the repeat dose 340 mg cohort, there were some individuals who did not achieve nadir IgG concentration until after the last dose, indicating they may have not reached steady state. In contrast, most subjects in the 680 mg cohort achieved nadir concentration prior to the last dose and maintained that response until after the last dose, indicating steady state response was achieved. Data from this study will be used to support dose selection in future studies.

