### **Open-Label Extension Objective:**

The objective of the OLE is to evaluate the effect of switching to a every 2-week dosing regimen of 340 mg RVT-1401 on all study endpoints.

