### **Open-Label Extension**

If the participant is eligible and consents to enroll into the OLE, starting at Week 8 an additional 3 doses of 340 mg RVT-1401 will be administered over a 6-week period (every 2 weeks) followed by a 6-week follow up period.

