Injection site reactions 			X			X	X	X	X				X		X	X					
MG-ADL 			X			X	X	X	X			X	X		X	X			X	X	
Quantitative Myasthenia Gravis (QMG) Score 	X	X			X	X	X	X				X	X		X	X			X	X	

	Screening 	Treatment Period Week 1 (Days)			Treatment Period Weekly Visit (Weeks)				Treatment Period Week 6 (Days)			OLE and Follow-up Period Weekly Visit (Weeks)							Early Withdrawal Visit	
		Day 1 (Baseline)	Day 3	Day 5	2 (Day 8)	3 (Day 15)	4 (Day 22)	5 (Day 29)	6 (Day 36)	Day 38	Day 40	7	8	9	10	12	14	16	18	
Study Timepoint (Weeks)	Within 21 Days																			
Time Window (days)			+1 day	+1 day	+/-1 day	+/-1 day	+/-1 day	+/-1 day	+/-1 day	+1 day	+1 day					+/-2 days	+/-2 days	+/-2 days	+/-2 days	+/-2 days
Myasthenia Gravis Composite (MGC) Score 		X			X	X	X	X				X	X			X	X			X
Myasthenia Gravis Quality of Life (MG- QOL15r) Score 		X						X								X	X			X
Satisfaction Questionnaire												X								X
Adverse events	X	X	X	X	X	X	X	X	X	X	X	X	X	X	X	X	X	X	X	
Concomitant medication	X	X	X	X	X	X	X	X	X	X	X	X	X	X	X	X	X	X	X	

1. Screening can take place over multiple days to ensure participants withhold cholinesterase inhibitors for at least 12 hours prior to the QMG and MGC assessments.
2. Consent for enrollment into the OLE must occur prior to Week 8.
3. Participants who complete the 6-week, randomized, double-blind treatment phase are eligible to participate in the OLE
4. Vitals, ECG and blood draws for safety, PK, and PD assessment will be collected pre-dose on dosing days where specified.
5. Pregnancy tests will be collected pre-dose (via urine dipstick) on dosing days where specified. Serum pregnancy tests should be collected at screening, week 18, and early withdrawal.
6. Participants positive for anti- RVT-1401 antibody at Week 18 will be requested to return at approximately 6, 9, and 12 months post-dose for additional samples or until their result is no longer positive. However, for purposes of safety follow-up and database lock participation ends at the Week 18 visit.
7. Local injection site reactions will be assessed at approximately 10 minutes post dose.
8. MG assessments will be assessed pre-dose when collected on dosing days.
9. Subjects should be instructed to withhold cholinesterase inhibitors for at least 12 hours prior to the QMG and MGC assessments.

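### The optional OLE tests compare groups at Weeks 8, 10 and 12, so they do not test change after switching, and no listed visit follows the third OLE dose

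*Protocol*

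**What the plan says.** **Question.** Protocol section 4: "The objective of the OLE is to evaluate the effect of switching to a every 2-week dosing regimen" of 340 mg, on all study endpoints.

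**Doses and samples.** Protocol 5.1: "starting at Week 8 an additional 3 doses of 340 mg RVT-1401 will be administered", one every 2 weeks, so at Weeks 8, 10 and 12. The footnotes to Protocol 8.2 say that "blood draws for safety, PK, and PD assessment will be collected pre-dose on dosing days where specified", and that MG scales on dosing days are also done before the dose.

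**Analysis.** Protocol 10.3.1 (OLE and Follow up Analyses) is mainly descriptive: "Descriptive Analyses will be presented by randomized treatment assignment from the double-blind treatment period and overall". It then allows a "two sample t-test or Chi-Square test, may be performed for the changes or shifts at weeks 8, 10, and 12 separately". The sentence opens "Ad hoc statistical analyses such as two sample t-test", and the next one reads: "The significance will be evaluated at a 0.05 two-sided level for informational purposes only". The section covers both the OLE population and the 12-Week Follow up Population.

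**SAP.** Section 5.2 sets the OLE baseline at the last value before the first OLE dose, normally the Week 8 pre-dose value. Section 5 puts OLE data in the same tables as double-blind data unless otherwise specified. Section 12 gives ANCOVA least-squares means with 95% CIs per group, and between-group t-tests, at each scheduled visit for the pharmacodynamic endpoints. No paired or within-participant OLE test is named, and section 14 does not withdraw the protocol's tests.

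**The concern.** Switching is a before-and-after question. With one OLE regimen and no concurrent control, the natural quantity is each participant's change from an on-treatment value to values on the new regimen. The named tests ask something else. The plan does not say which two samples are meant, and no reading addresses switching well:

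- Prior arm against prior arm: the null is equal change in the arms, not absence of change.
- Visit against visit: the right contrast, but the pairing is discarded.
- OLE participants against those who declined: the groups are self-selected.

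The listed visits also miss the end of OLE dosing, and the SAP's OLE baseline follows a dosing gap. At stake is how the OLE results are read when judging less frequent dosing. Equal loss of effect in both active arms would give a non-significant comparison that could be taken for a maintained effect. Comparing prior-active with placebo switchers would largely show that the latter had started drug.

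**Working it through.** The documents give no sample size, effect or power for the OLE tests, so there is no stated figure to reproduce.

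**1. Visits against doses.** The schedule labels Week 2 as Day 8 and Week 6 as Day 36, so day = 7 × (week − 1) + 1.

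| Visit | Day | OLE doses before the sample | Listed test visit |
|---|---|---|---|
| Week 7 | 43 | 0 (7 days after last weekly dose) | no |
| Week 8 | 50 | 0 | yes |
| Week 10 | 64 | 1 | yes |
| Week 12 | 78 | 2 | yes |
| Week 14 | 92 | 3 | no |

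Protocol 3.2.3.3 puts the IgG nadir after a single SC dose at days 8–15 in most individuals. Counting the Day 78 dose as day 1, that is Days 85–92, so Week 14 captures dose 3 and Week 12 cannot. The protocol's own expectation for placebo switchers is timed there: they are "expected to achieve an IgG reduction of approximately 35-45% after the last OLE dose". Measured from the SAP 5.2 OLE baseline, the Week 8 change is normally zero for everyone and a t-test on it is undefined (0/0). Measured from study baseline, Week 8 reflects only the double-blind regimen.

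**2. Reference visit.** Protocol 3.2.2 (Expected Treatment Effect) says IgG will rise between Week 6 and the start of OLE dosing at Week 8. In prior-active participants, change from Week 8 therefore starts from a partly recovered level and could make less frequent dosing look better than it would against an on-treatment value such as Week 7.

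**3. What a two-sample test detects (illustration).** Assume 7 per arm (21 allocated 1:1:1, all entering the OLE), two-sided alpha 0.05, and the SD of 20 from Protocol 10.1, which is for double-blind Week 7. The within-participant correlation ρ is not given; take 0.5, 0.7 and 0.8. Then SD of change = 20 × √(2(1 − ρ)) = 20.0, 15.5 and 12.6 points.

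- Both active arms change equally: the difference is 0, so rejection is 5% for any size of change.
- Arms change by 15 and 25 points: noncentrality = 10 / (SD × √(2/7)), 12 df; power 28%, 20% and 14% at SD 12.6, 15.5 and 20.

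**4. What a paired test detects (illustration).** Noncentrality = d × √n / SD, with n − 1 df. Protocol 3.2.2 expects trough IgG 15–25% above nadir, which can be read in two ways:

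- Percentage points of baseline: d = 15 to 25.
- Relative to nadir: expected reductions of 75–80% and 65–70% leave nadirs of 20–35% of baseline, so d = 0.15 × 20 = 3 up to 0.25 × 35 = 8.75, about 9.

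| Reading | n = 7, one arm | n = 14, active arms pooled |
|---|---|---|
| d = 15–25 | 39–99% | 74–100% |
| d = 3–9 | 6–35% | 8–69% |

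The low end of each range is the smallest d with SD 20 (for n = 7: 15 × 2.646 / 20 = 1.98, giving 39%). The high end is the largest d with SD 12.6.

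**The case against.** The strongest reply is that these tests carry little weight. They are ad hoc, introduced by such as and may, and informational, so a paired test is not excluded. That stands, and it limits the severity.

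A reader might infer that the OLE analysis cannot answer the switching question. The documents do not support that. The main analysis is descriptive, by prior arm and overall, and the SAP's OLE baseline makes the summarised changes within-participant. SAP sections 5 and 12 together arguably give visit-wise means with 95% CIs by prior arm, including Week 14 for total IgG and anti-AChR, so a loss in both active arms should be visible. Weeks 10 and 12 each close a full 2-week interval and do inform on the regimen. Still missing is an estimate, with its CI, of each participant's change from an on-treatment visit.

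A reader might also call it a false-positive problem when placebo switchers fall and a prior-active arm does not. The null tested, equal change, is then false, so rejection is power. The fault is that the result answers a different question.

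The sentence also serves the 12-Week Follow up Population. There, comparing randomised arms off drug is reasonable and Week 8 is informative, so the tests should not simply be deleted. Finally, equal loss in both active arms is not what the protocol predicts: Protocol 3.2.2 expects exposure to fall about 8–10-fold for Regimen A and 1–2-fold for Regimen B. That case shows what the test is blind to; it is not a forecast.

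**Conclusion.** The point holds in a limited form. The named OLE tests do not test change after switching, the Week 8 test carries no OLE information for OLE participants, and no listed visit follows dose 3. These follow from the text and schedule without numerical assumptions. The descriptive summaries partly fill the gap, but from a Week 8 baseline they do not directly compare every-2-week with weekly dosing in prior-active participants.

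The 5% rejection under equal change holds for any SD. The paired-power figures are illustrative only: they rest on a borrowed SD, an assumed correlation, full OLE entry and the reading of the 15–25% rise. On the relative reading, a single arm of 7 would usually miss the change even with a paired test, so the gain is an estimate of the right quantity rather than assured power. No primary or secondary conclusion is affected. This is a low-cost improvement to an informational analysis.

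**What to change.** In Protocol 10.3.1 (OLE and Follow up Analyses), with matching SAP text:

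- **OLE population:** estimate within-participant change with a 95% CI, by double-blind arm and with the two active arms pooled. A paired t-test, or an exact McNemar test for responder status, may accompany it for information only.
- **Reference:** Week 7 for prior-active participants; Week 8 pre-dose for placebo switchers, or the last value before the first OLE dose if a scale is not scheduled then.
- **Visits:** Weeks 10, 12 and 14 for total IgG and anti-AChR; Weeks 10, 12 and 18 for the MG scales, as far as the schedule can be read. For the scales the only visit after dose 3 is Week 18, 6 weeks later, so that gap is not fully closed.
- **Week 8 test:** drop it for the OLE population only. Keep the between-arm comparison for the 12-Week Follow up Population.
- **Power:** label any figure illustrative and show both readings of the expected rise.

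**Cost:** a protocol wording change as well as SAP text; no new samples or visits. There is still no concurrent control, and Week 7 is 7 days after a dose while Weeks 10, 12 and 14 are 14 days after one. The contrast therefore mixes regimen with time since dose and remains descriptive.

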## **11. ADVERSE EVENTS (AE) AND SERIOUS ADVERSE EVENTS (SAEs)**

The Principal Investigator or site staff is responsible for detecting, documenting and reporting events that meet the definition of an AE or SAE. All SAEs must be reported to the Sponsor within 24 hours of awareness of the event (Section 11.2).

Once former study participants have completed the study, the Principal Investigator is not obligated to actively seek AEs or SAEs. However, if the Principal Investigator learns of any SAE, including a death, at any time after a participant has been discharged from the study, and he/she considers the event reasonably related to the investigational product or study participation, the Principal Investigator must promptly notify the Sponsor.

